## 1 Introduction and rationale

Lung nodules are highly prevalent in the population, and percutaneous lung puncture (PLP) is one of the gold standards for the qualitative diagnosis of lung nodules. Cone-beam CT (CBCT) plays a critical role in guiding percutaneous lung puncture. However, the poor quality of CBCT imaging can complicate the procedure, especially in certain patient populations. Improving the quality of CBCT images may increase the success rate of CBCT-guided lung nodule puncture procedures, reduce radiation exposure, and minimize the number of punctures. Although several previous studies have used generative deep learning methods to improve CBCT image quality, no prospective clinical trials have yet validated the practical application of these models. In this study, a Generative AI-Powered Puncture Surgery Navigation System for lung punctures (GPS-Lung) systems constructed based on the synthesis CT (sCT) images and intraoperative guidance system, and a prospective cohort is used to validate its efficacy in clinical practice.

## 2 Objectives

- To construct a GPS-Lung system to improve CBCT imaging quality in clinical practice and evaluate the integration of GPS-Lung system to guide lung puncture surgery, with the goal of improving puncture surgery efficiency, reducing radiation exposure, and minimizing procedural complications.

## 3 Study design

This study used a prospective randomized controlled study design. Participants scheduled to undergo percutaneous lung puncture were included and randomly assigned in a 1:1 ratio to either the GPS-Lung system guided puncture group or the CBCT-guided puncture group.

## **Study Protocol**

Study type: Prospective randomized controlled trial.

Study schedule: January 2025-May 2025 (5 months total).

Study location: Three Level 3A hospitals in China (Wuhan Union Hospital, Wuhan Union West Hospital, and Wuhan Union Jinyinhu Hospital).

## **4 Study population**

### **4.1 Study population**

Participants scheduled to undergo CBCT-guided lung puncture.

### **4.2 Inclusion criteria**

- Participants require CBCT-guided PLP and meet the indications for the procedure.
- Participants have pre-operation CT images.
- Participant's physical condition is suitable for PLP.

### **4.3 Exclusion criteria**

- Participants have a history of allergy or serious adverse reaction to iodine contrast media or other related drugs.
- Participants are pregnant or breastfeeding.
- Participants are unwilling or unable to provide informed consent.

## **5 Study process**

**Group:** A Web-based platform was used to randomize patients into experimental group or control group.

Experimental group: Percutaneous lung puncture procedure using GPS-Lung system guidance.

Control group: Percutaneous lung puncture procedure using CBCT guidance.

**Observation indicators:** The number of puncture needles, radiation dose, puncture time and intraoperative and postoperative complications within 7 days.

## 6 Randomization and binding

### 6.1 Randomization

Randomization was performed using a Web-based system (<https://www.randomizer.org/#randomize>) that employed computer-generated, permuted-block sequences, with stratification by center. Notably, the Web-based central randomization service ensured concealment of trial-group assignments.

### 6.2 Binding

This study conducted a double-blind design to ensure that neither participants nor researchers were aware of the group assignments throughout the study. Participants, researchers, data collectors, and outcome assessors were blinded to the group allocation. Statisticians and authors were unaware of the subgroups during data analysis. Doctors, technicians and trial nurses were aware of the subgroups but were not involved in data collection or analysis.

For image quality and lesion quality scoring, we will give a mixture of CBCT, sCT, and CT images to the scorers, and they unaware of the images type.

## 7 Observation outcomes

### 7.1 Primary outcome

Puncture times of participants for GPS-Lung system and CBCT-guided lung puncture procedures. Puncture times was defined as the number of punctures performed throughout the PLP procedure.

### 7.2 Secondary outcomes

Radiation dose, duration of surgery and intraoperative and postoperative complications

within 7 days of participants for GPS-Lung system and CBCT-guided lung puncture procedures.

### **7.3 Other outcomes**

Algorithmic performance for image quality enhancement and doctors' scoring of image and lesion quality.

## **8 Complications**

Potential complications are listed below:

Pneumothorax: Air may enter the pleural cavity after a lung puncture, causing the lung atrophy.

Bleeding: Puncture of lung tissue may result in bleeding within the lung or chest cavity.

Pneumonia: The puncture procedure may trigger an infection, which can result in pneumonia.

Atelectasis: Airway obstruction or atrophy of lung tissue may cause partial atelectasis.

Intercostal neuralgia: The puncture procedure may irritate the intercostal nerves, resulting in postoperative pain.

Lung abscess: Both intraoperative and postoperative infections may lead to localized abscess formation.

Air embolism: Intraoperative entry of puncture gas into the vessel resulting in air embolism.

## **9 Sample size estimation**

The sample size calculation in this study was estimated based on the number of intraoperative lung punctures. A total of 38 participants received CBCT-guided PLP from retrospective cohort were included from Wuhan Union Hospital. The mean (SD) puncture times of these patients were  $2.3 \pm 2.2$ . We used a 2.5% one-sided significance

## Study Protocol

level with 90% efficacy for sample allocation on a 1:1 basis. The sample size was calculated based on the following formula:

$$n = \frac{2(Z_{\alpha/2} + Z_{\beta/2})^2 * \sigma^2}{\Delta^2}$$

n represents the sample size of each group.  $Z_{\alpha/2}$  represents the critical value of the significance level ( $\alpha$ ), and the  $\alpha=0.025$  in the study.  $Z_{\beta/2}$  represents the critical value of efficacy (1 -  $\beta$ ), and the  $\beta=0.9$  in the study.  $\sigma^2$  represents the within-group variance. In the current,  $\sigma$  was substituted by the standard deviation of puncture times from 38 participants.  $\Delta$  represents the smallest difference between the means of the two groups. In the current, the  $\Delta$  was considered as 1. Therefore, the sample size to be included in this study for each group is 103. We will included 220 participants (each group 110 participants).

## 10 Data analysis program

The baseline comparisons between the two groups, appropriate statistical tests will be employed based on the type of data (parametric or non-parametric). Categorical variables will be analyzed using the Chi-squared test or Fisher's exact test, while continuous variables will be analyzed using the *t*-test or the Mann-Whitney U test. Paired *t*-tests will be used to compare the means of the scores for overall image quality and lesion visualization between paired groups. The weighted kappa coefficient ( $\kappa$ ) or kendall coefficient of concordance (W) or intra-class correlation coefficient (ICC) will be used to assess the agreement of the image quality of all samples and the lesions score of sCT among different readers.

## 11 Data management and monitoring

Data management: All data will be anonymized and stored in a secure, specialized database (Picture Archiving and Communication Systems, PACS) to ensure data integrity and confidentiality. Researchers can access it in PACS. Data will be kept for a

period of 15 years. Imaging data is evaluated independently by an imaging assessment team.

**Data monitoring:** An independent Data Safety Monitoring Committee (DMC) will be established to regularly review the progress, safety, and overall quality of the trial.

## **12 Ethical considerations**

### **12.1 Ethical approved**

The study will be registered with the Clinical Trial Registry. This study has been approved by the ethics committees of the Wuhan Union Hospital (Reference number: UHCT-IEC-SOP-016-03-01).

### **12.2 Informed consent**

All participants will be requested to sign an informed consent form prior to participation in the trial. The consent form will provide the participants with a clear explanation of the purpose of the study, potential risks, and possible benefits. Participants have the right to withdraw from the study at any time, without any impact on their subsequent treatment.

## **13 Schedule of the trial**

January-March 2025: Trial initiated, ethical approval granted, and patient recruitment initiated. Data collection for participant recruitment and scanning completed.

April-May 2025: Data analysis and summary report.

## **14 Discussion**

In this study, the efficacy of the GPS-Lung system in guiding percutaneous lung

puncture procedures was comprehensively evaluated through a prospective randomized controlled trial. The expected results will provide strong evidence for the clinical application of GPS-Lung system to improve the success rate of percutaneous lung puncture procedures, while reducing the radiation exposure and minimize complications for patients.

## 1 Introduction and rationale

Lung puncture biopsy is the gold standard for qualitative diagnosis of pulmonary nodules. There are various techniques for performing lung puncture biopsy, among which cone beam CT (CBCT)-guided percutaneous lung puncture (PLP) has emerged as a novel approach in recent years. Compared with conventional CT-guided lung puncture biopsy, CBCT reconstructs a CT-like images while offering the advantages of reduced radiation dose exposure. Additionally, CBCT-guided lung puncture biopsy is performed in real-time under the fluoroscopic guidance using the DSA, which not only enhances procedural efficiency but also minimizes radiation damage to the patient. However, one limitation of CBCT is its relatively poor image quality. This becomes particularly problematic in cases involving small nodules or nodules adjacent to vital organs or blood vessels, as the poor image quality may affect the procedural accuracy, potentially leading to failed puncture or serious complications. Therefore, improving the quality of CBCT images is crucial to enhancing the efficacy of CBCT-guided lung puncture biopsy procedures and reduce complications.

Artificial Intelligence (AI) has been heavily researched in image segmentation and generation and has demonstrated promising results. In particular, generative models such as Generative Adversarial Networks (GANs) and diffusion models have shown potential in enhancing the quality of images and transforming multimodal images. Previous studies have been conducted to improve CBCT image quality through generative AI models and have demonstrated that these models can effectively improve CBCT image quality, achieving quality comparable to that of conventional CT images. These studies demonstrate the great potential of generative AI in improving the quality of CBCT images particularly in guiding lung puncture procedures. However, AI has barely been used in guiding clinical surgical practice. This is mainly due to the

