## Statistical Analysis Plan

heterogeneity of clinical data used in daily practice, with the datasets used for training AI algorithms often being considered unrepresentative of real-world clinical conditions. Therefore, prospective clinical trials are essential to validate the applicability of AI in clinical applications. As with any medical innovation, clinical trials are indispensable for attributing tangible benefits to the employment of AI in CBCT-guided lung aspiration biopsy procedures.

A generative AI model was developed by retrospectively analyzing data from 3106 participants who underwent CBCT-guided lung puncture biopsy procedures, which the aim of improving the quality of CBCT images. Then, a Generative AI-Powered Puncture Surgery Navigation System for lung punctures (GPS-Lung) system is constructed based on the synthesis CT (sCT) images and intraoperative guidance system. We raised a question: Can GPS-Lung system contribute to the improvement of clinical lung puncture procedures? The application of GPS-Lung system to guide lung puncture procedures can improve the procedural efficacy, reduce radiation exposure, and minimize surgical complications, thereby providing tangible benefits to patients. To validate the clinical applicability of the constructed GPS-Lung system, a follow-up prospective randomized controlled trial (RCT) was conducted to compare the surgical outcomes, radiation dose, and complications rates between conventional CBCT-guided lung puncture procedures and GPS-Lung system guided lung puncture procedures.

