## Statistical Analysis Plan

### 3.2 Inclusion and exclusion criteria

#### Inclusion criteria

- Participants who require CBCT-guided PLP and meet the clinical indications for the procedure.
- Participants with pre-operation CT images available.
- Participants whose physical condition is suitable for PLP.

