### 3.3 Randomization and binding

Randomization will be performed using a web-based system, employing computer-generated permuted-block sequences with stratification by center. Notably, this centralized, web-based randomization service ensures concealment of trial-group assignments.

A double-blind design will be conducted to ensure that neither participants nor researchers will be aware of group allocation during this study. Participants, researchers, data collectors and outcome assessors will be blinded to group assignment. Statisticians and authors will be also blinded to subgroup allocation during data analysis. Doctors, technicians and trial nurses will be aware of subgroup assignments but will not be involved in data collection or analysis.

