## Statistical Analysis Plan

### 5.5 Primary and secondary study parameter(s)

For primary outcome, secondary outcomes and baseline comparisons between the two groups, appropriate statistical tests (parametric or non-parametric) will be applied to categorical variables (Chi-squared test/Fisher's exact test) or continuous variables (*t*-test, Mann-Whitney U test).

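### The primary comparison ignores nodule size and location, although the SAP says poor image quality matters most there and every participant has a CT from which to read them

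*SAP*

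**What the plan says.** **Rationale.** SAP section 1 begins with a general weakness, "However, one limitation of CBCT is its relatively poor image quality", and then says where it weighs most: "This becomes particularly problematic in cases involving small nodules or nodules adjacent to vital organs or blood vessels". Protocol section 1 makes the same graded statement without naming the group: "the poor quality of CBCT imaging can complicate the procedure, especially in certain patient populations".

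**Question.** It is put for lung puncture as a whole: "Can GPS-Lung system contribute to the improvement of clinical lung puncture procedures" (SAP section 1). The objectives in both documents are equally general.

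**Eligibility.** SAP section 3.2 admits "Participants who require CBCT-guided PLP and meet the clinical indications for the procedure", with no condition on nodule size or position. It also requires "Participants with pre-operation CT images available". Protocol section 4.2 agrees.

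**Randomisation.** SAP section 3.3: "employing computer-generated permuted-block sequences with stratification by center". Centre is the only factor.

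**Analysis.** For the primary outcome, the secondary outcomes and baseline alike, SAP section 5.5 says "appropriate statistical tests (parametric or non-parametric) will be applied to categorical variables (Chi-squared test/Fisher's exact test) or continuous variables", naming the t-test and Mann-Whitney test for the continuous ones. Protocol section 10 lists the same tests. Neither document plans a covariate, subgroup or interaction, and nodule size and location appear nowhere in the eligibility, stratification, endpoint or analysis text.

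**The concern.** On the SAP's own reasoning, a small nodule or one close to a vessel is harder to hit under poor images. Difficulty should therefore predict the number of punctures, and it may also modify the benefit of better images. Leaving it out of the analysis has three consequences.

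- Variance that a baseline measurement could remove stays in the primary comparison.
- Stratification by centre does not balance difficulty, so a chance excess of hard nodules in one arm shifts the unadjusted estimate, and no adjusted estimate is planned.
- With no prespecified interaction, a null result cannot be told apart from a benefit limited to hard nodules, and any later statement about hard nodules would be post hoc.

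**Working it through.** **Inputs.** From SAP section 3.4: control mean 2.3 and SD 2.2 punctures (38 historical CBCT-guided patients), difference 1, one-sided alpha 0.025, target power 90%, 103 per arm raised to 110. Not in the documents, so assumed: the share of variance R² explained by nodule features (0.1 to 0.3), and the share f of difficult nodules.

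**1. The plan's figure.** Normal approximation: n = 2(1.960 + 1.282)² × 2.2² / 1² = 101.7, so 102 per arm. Noncentral-t power is 0.898 at 102 and 0.901 at 103, so 103 is right and matches the SAP's software output of 0.90089. At 110 per arm, power is 0.919.

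**2. Gain from adjustment.** Residual SD = 2.2 × √(1 − R²). The standard error of the arm difference is that SD × √(2/110). Power is by noncentral t, ignoring the few degrees of freedom spent on covariates.

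| R² (assumed) | Residual SD | SE | Power at difference 1 |
|---|---|---|---|
| 0 | 2.20 | 0.297 | 0.919 |
| 0.1 | 2.09 | 0.281 | 0.943 |
| 0.2 | 1.97 | 0.265 | 0.963 |
| 0.3 | 1.84 | 0.248 | 0.980 |

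**3. Chance imbalance.** Take f = 0.5. The difference between arms in the proportion of difficult nodules has SD √(2 × 0.5 × 0.5 / 110) = 0.067. A gap of at least 10 percentage points in either direction is 0.10/0.067 = 1.48 SDs, a probability of about 14%. If a yes/no difficulty indicator explains R² of the variance, the mean gap between difficult and easy nodules is 2.2 × √R² / 0.5, which is 1.39 punctures at R² = 0.1 and 2.41 at 0.3. A 10-point imbalance then moves the unadjusted difference by 0.14 to 0.24 punctures, or 14% to 24% of the planned effect.

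**4. What an interaction can show.** SE = 2.2 × √(2/(110f) + 2/(110(1 − f))), two-sided 0.05, normal approximation.

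| f (assumed) | SE | Power if effects differ by 1 | Power if effects differ by 2 |
|---|---|---|---|
| 0.5 | 0.59 | 0.39 | 0.92 |
| 0.3 | 0.65 | 0.34 | 0.87 |

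**5. Is dilution shown?** If a 1-puncture benefit existed only in a share f and were zero elsewhere, the average effect would be f, and power at 110 per arm would be 0.77 at f = 0.8 and 0.39 at f = 0.5. The documents give neither f nor a zero effect elsewhere. The SAP defines its difference of 1 as a difference between group means, which already averages over everyone enrolled. An average of 1 is also arithmetically possible in a mixed population. Suppose each procedure needs at least one puncture, half the patients average 1 and half average 3.6, for an overall mean of 2.3. An effect of 2 in the harder half, out of 2.6 removable punctures, then gives an average of 1.

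**The case against.** The strongest reply is that nothing here is invalid. Randomisation makes the unadjusted test sound, its type I error already allows for chance imbalance, and the trial asks a general question that all-comer enrolment answers well. SAP section 1 itself complains that AI training data are often seen as unrepresentative of practice, which favours broad entry. At the planned effect, adjustment adds only 2 to 6 percentage points to adequate power, on an R² with no source. The interaction would miss a 1-puncture difference in effect more often than not. Image quality and lesion visualisation are also compared separately in SAP section 5.6, so the imaging link is not wholly unexamined.

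Most of this stands, and it rules out two stronger conclusions that a reader might draw.

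- *That the SAP confines the benefit to difficult nodules, so enrolling everyone dilutes the effect.* The wording is graded and follows a statement of a general limitation. The planning mean and SD come from a CBCT cohort with no stated nodule selection. Power figures for smaller effects also depend on the SD chosen. With SD 2.2 in both arms, power is 0.77 at a difference of 0.8 and 0.59 at 0.65. If treatment instead removes a constant fraction of each patient's punctures beyond the first, the treated-arm SD shrinks (to 0.85 and 1.10) and power is about 0.94 and 0.79.
- *That the trial cannot test its own rationale.* It tests the general one; only the nodule-specific part goes unexamined.

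The objection does not justify leaving the covariates out. A valid test can still be less precise than it need be, and here the extra information comes from a scan that everyone has.

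**Conclusion.** The point holds as an avoidable weakness of the analysis, not as an error that invalidates it. The SAP identifies nodule size and proximity to vital structures as the conditions under which the problem is worst, requires a CT that shows both, and then uses neither.

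At the planned difference the gain in power is modest. It would be larger in absolute terms if the true effect were smaller: at 0.65 punctures with SD 2.2 in both arms, adjustment takes power from 0.59 to 0.63-0.74 for R² of 0.1 to 0.3. That scenario is illustrative and appears nowhere in the documents. Steadier estimates under imbalance, and a subgroup contrast declared in advance, are worth at least as much as the power.

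Every figure for the gain rests on the assumed R². The imbalance and interaction figures also rest on the assumed share of difficult nodules and a common SD of 2.2. No case is made for restricting entry or enlarging the trial.

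**What to change.** In SAP section 5.5, with a matching sentence in Protocol section 10:

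1. **Primary analysis.** Replace the open choice of two-group test for puncture count with a regression on arm, adjusted for centre (the stratification factor), nodule diameter (continuous) and adjacency to vital organs or vessels (yes/no). Read both nodule features from the pre-operation CT before randomisation.
2. **Form.** Report the adjusted difference in mean punctures with a 95% CI, using robust standard errors or deriving it from a count model. State which in advance. The count is skewed: it cannot be negative, and its SD (2.2) is nearly as large as its mean (2.3).
3. **Supportive analysis.** Prespecify one arm-by-difficulty interaction, where difficult means small or adjacent, with the size cut-off and the definition of adjacency fixed in advance. Report the effect and 95% CI in each group. Label it supportive and state its limited power.

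The cost is two baseline fields, a slightly longer analysis, and an interaction that will be imprecise. The main analysis can keep the existing one-sided 0.025 level.

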## Statistical Analysis Plan

heterogeneity of clinical data used in daily practice, with the datasets used for training AI algorithms often being considered unrepresentative of real-world clinical conditions. Therefore, prospective clinical trials are essential to validate the applicability of AI in clinical applications. As with any medical innovation, clinical trials are indispensable for attributing tangible benefits to the employment of AI in CBCT-guided lung aspiration biopsy procedures.

A generative AI model was developed by retrospectively analyzing data from 3106 participants who underwent CBCT-guided lung puncture biopsy procedures, which the aim of improving the quality of CBCT images. Then, a Generative AI-Powered Puncture Surgery Navigation System for lung punctures (GPS-Lung) system is constructed based on the synthesis CT (sCT) images and intraoperative guidance system. We raised a question: Can GPS-Lung system contribute to the improvement of clinical lung puncture procedures? The application of GPS-Lung system to guide lung puncture procedures can improve the procedural efficacy, reduce radiation exposure, and minimize surgical complications, thereby providing tangible benefits to patients. To validate the clinical applicability of the constructed GPS-Lung system, a follow-up prospective randomized controlled trial (RCT) was conducted to compare the surgical outcomes, radiation dose, and complications rates between conventional CBCT-guided lung puncture procedures and GPS-Lung system guided lung puncture procedures.

